7.2.1. Definitions of Clinical Outcomes

Objective Response Rate (ORR)

Objective response rate defined as the proportion of patients achieving complete or partial response on palbociclib combination therapy.

Clinical Benefit Rate (CBR)

Clinical benefit rate is defined as the proportion of patients achieving complete or partial response, or stable disease ≥ 24 weeks on palbociclib combination therapy. Stable disease will be defined as no evidence of complete or partial response, and no progression on palbociclib therapy for 24 weeks or greater.

CCI [Redacted]

[Redacted]

Progression Free Survival (PFS)

Progression Free Survival is defined as the time from palbociclib combination treatment initiation until the earliest of (1) clinician-documented progression while on palbociclib (2) death, (3) start of a new therapy line after final palbociclib dose if the reason for discontinuation of palbociclib was disease progression, or (4) last available follow-up. Patients who did not experience a progression event (items 1, 2 and 3) will be censored at date of last available follow-up. PFS (in months) will be calculated as (first event date - palbociclib initiation date + 1)/30.4.

PFS will be analysed using a Kaplan-Meier (KM) survivor function. A table will show the survivor rate at 3 month intervals and will also show the 3 month incremental survivor rate, ie, the survivor rate from the start of that 3 month interval rather than from time zero. The median survival (if the median is reached) and a KM chart will also be shown. Time zero will be taken at the point of palbociclib initiation.

CCI [Redacted]

[Redacted]

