- Agrees to participate in the study and complete the CRFs.

¹ Breast surgeons/general surgeons/gastro-surgeons may also be included as relevant treaters in Japan.

Patient inclusion criteria

- ≥ 18 years old;
- HR+/HER- breast cancer diagnosis with confirmed metastatic or advanced disease;
- Received palbociclib plus letrozole/aromatase inhibitor or palbociclib plus fulvestrant in line with the licenced indication(s);
- No prior or current enrolment in an interventional clinical trial for ABC/MBC;
- Minimum of three months of follow up data since palbociclib with fulvestrant initiation, or minimum of six months of follow up data since palbociclib with letrozole/aromatase inhibitor initiation (core medical record review);
- Minimum of three months of follow up data since palbociclib initiation (German interim medical record review only);
- Inoperable or recurrent breast cancer (Japan only).

In order to ensure that sufficient data is captured for each indication, indication soft quotas will be enforced. This will be determined on a country by country basis.

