- Line of therapy that palbociclib is received (T);
- Treatments received in the line of therapy prior to palbociclib (T-1);
- Treatments received in the line of therapy post palbociclib (T+1).

Palbociclib dosing characteristics**To be abstracted directly from the medical records:**

- Palbociclib starting dose;
- Reasons for starting at a dose lower than 125 mg/day;
- Number of palbociclib dose changes;
- Details of each dose change (eg, dose increase, dose decrease, dose interruption, cycle delay);
- Date of dose change;
- Reason for dose change (eg, side effects/toxicity, lack of response);
- Status of combination partner therapy at dose change (eg, if continued or stopped).

To be derived

- Time from palbociclib initiation to first dose change;
- Duration of dose interruption;
- Duration of cycle delays.

Supportive therapies received during palbociclib treatment**To be abstracted directly from the medical records:**

- Supportive therapies received during palbociclib treatment.

Clinical Outcomes**To be abstracted directly from the medical records:**

- Initial response recorded;
- Time from palbociclib initiation to initial response;
- Frequency with which response to palbociclib was assessed;
- Proportion with complete response;
- Proportion with complete response defined by radiological evidence;
- Proportion with partial response defined by radiological evidence;
- Time from palbociclib initiation to complete response;
- Proportion with partial response;
- Time from palbociclib initiation to partial response.

To be derived

- Objective response rate defined as the proportion of patients achieving complete or partial response on palbociclib;
- Clinical benefit rate defined as the proportion of patients achieving complete or partial response, or stable disease ≥ 24 weeks on palbociclib. Stable disease will be defined as no evidence of complete or partial response, and no progression on palbociclib therapy for 24 weeks or greater;
- Proportion with stable disease ≥ 24 weeks on palbociclib;

█ [REDACTED]

- Progression free survival (if applicable) defined as the time from the start of palbociclib to the first subsequent progression or death;
- Time to death, defined as the time from the start of palbociclib to death;

█ [REDACTED]

- Progression free at 3, 6, 12, 18, 24 months defined as the proportion of patients who have no documented progression at defined time points;

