6. HANDLING OF MISSING VALUES

Subjects with missing values for a particular endpoint will not contribute to the analysis of that endpoint. Missing data will not be imputed.

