7.2. Statistical Methods

Based on the descriptive nature of the study, all study measures will be summarized descriptively through the tabular and graphical display of mean values, standard deviations, and ranges for continuous/numeric variables of interest. For categorical variables, frequency distributions (n, %) will be displayed. Missing and unknown categories for each variable also will be presented. Percentages will be calculated excluding missing values. All endpoints will be calculated for the overall population and by the stratification variables listed in [Section 4.3](#) (sample sizes permitting).

To show how one treatment line moves to the next, adjacent treatment combinations will be cross-tabulated (showing frequencies), eg, treatments received in the line prior to palbociclib (T-1) will be cross-tabulated with treatment line at which palbociclib was received (T), T will be crossed by treatments received at the line following palbociclib (T+1) and T+1 will be crossed by treatments received at the second line following palbociclib (T+2.)

For each of the 4 lines, whether or not that line is still ongoing or not will be described (this excludes T-1 as that line cannot be ongoing). For those not still ongoing (ie, the line has ended), the reason for ending will be described.

Time-to-event outcomes (ie, time to treatment start, time to dose reduction, treatment duration, CCI, PFS, death) will be described using the Kaplan-Meier method. In addition to reporting median event times for these measures, time-dependent event rates (eg, proportion of patients without event at various time points from a starting point of interest) will also be reported based on lifetables derived from the Kaplan-Meier analyses. All analyses will be conducted using Stata (version 14.2 or higher) statistical software and IBM SPSS Survey Reporter.

The outlined statistical methods anticipate that the selected sample is randomly drawn from normally distributed populations. However, this study will employ a convenience sample; thus, results may not be generalizable to the entire universe of patients receiving palbociclib.

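### Clinical benefit rate needs 24 weeks of stable disease, but fulvestrant patients are eligible at 3 months and the SAP names no evaluable denominator; read literally, the fulvestrant rate is biased down

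*SAP*

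**What the plan says.** SAP 7.2.1 defines CBR as the proportion of patients with complete response, partial response, "or stable disease ≥ 24 weeks on palbociclib combination therapy". Stable disease means no response and "no progression on palbociclib therapy for 24 weeks or greater". SAP 5.5 repeats both definitions and adds a separate derived variable, "Proportion with stable disease ≥ 24 weeks on palbociclib".

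The patient inclusion criteria for the core review (SAP section 3; protocol 8.2.1) differ by combination partner: "Minimum of three months of follow up data since palbociclib with fulvestrant initiation", or a "minimum of six months of follow up data since palbociclib with letrozole/aromatase inhibitor initiation". The full analysis set (SAP 4.1) takes every eligible core-review patient and asks for no further follow-up.

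For missing data, SAP section 6 says "Subjects with missing values for a particular endpoint will not contribute to the analysis of that endpoint", and SAP 7.2 says "Percentages will be calculated excluding missing values". PFS has its own censoring rule in 7.2.1. The readable CBR text has neither a censoring rule nor an evaluable denominator, and the readable part of the Kaplan-Meier list in 7.2 does not name CBR. SAP 3.1 lists CBR under primary objective 6, subject to feasibility. SAP 4.3 plans stratification by combination partner.

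**The concern.** A fulvestrant patient whose record is reviewed between weeks 13 and 23, still on treatment, stable and progression-free, meets the inclusion criteria but cannot yet meet the stable-disease part of CBR. The SAP does not say how she enters the rate, and the two treatments its wording most readily allows both cause trouble.

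- **Literal definition.** She has not reached 24 weeks, so she stays in the denominator and out of the numerator. Incomplete observation is scored as lack of benefit.
- **Dropped as missing.** She leaves the denominator, while patients who progressed or responded equally early stay in it. The denominator then depends on outcome.

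AI patients all clear 24 weeks by design, so the distortion falls on fulvestrant alone. It would therefore appear in the AI versus fulvestrant results, and between countries with different follow-up, as an apparent difference in benefit. Two analysts following the same SAP could also report different CBRs from identical data.

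**Working it through.** **Core sample size.** The country counts in protocol Table 2 sum to 3131. Removing the 257 German interim records, which carry no clinical outcomes, gives 3131 − 257 = 2874, the core figure in SAP 2.1.1. That is the largest possible CBR denominator. No document gives the fulvestrant share, the follow-up distribution or an expected CBR.

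**Follow-up against the threshold**, using the SAP's 30.4 days per month ("PFS (in months) will be calculated as (first event date - palbociclib initiation date + 1)/30.4"):
- Threshold: 24 weeks = 168 days; 168/30.4 = 5.53 months.
- Fulvestrant minimum: 3 × 30.4 = 91.2 days = 13.0 weeks, which is 11.0 weeks short.
- AI minimum: 6 × 30.4 = 182.4 days = 26.1 weeks, which clears it.

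**Illustrative target.** Assume exponential PFS with the fulvestrant-combination medians quoted in the documents: 9.2 months (SAP section 2) and 10.8 months (protocol section 6). S(t) = 2^(−t/median).

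| Median | S(3 months) | S(24 weeks) |
|---|---|---|
| 9.2 | 0.798 | 0.659 |
| 10.8 | 0.825 | 0.701 |

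Ignoring responders who progress before week 24, the CBR with full follow-up is about S(24 weeks), or 66-70%.

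**Assumptions.** Let f be the share of fulvestrant patients with 3 months to under 24 weeks of follow-up, spread evenly over that interval, and r the share of them who have responded. I take f = 10% and 20%, and r = 15% to 25%. Neither comes from the documents.

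**Literal reading.** Reported CBR = (1 − f)·S + f·r, so the shortfall is f·(S − r).
- f = 10%: from 0.1 × (0.659 − 0.25) = 4.1 to 0.1 × (0.701 − 0.15) = 5.5 points.
- f = 20%: from 8.2 to 11.0 points.

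**Dropping only ongoing stable patients.** Reported CBR = [(1 − f)·S + f·r] / [1 − f·(A − r)], where A is the mean of S(t) over the interval (0.726 and 0.761 for the two medians). Example with median 9.2, f = 10%, r = 15%: (0.5935 + 0.015)/(1 − 0.0576) = 0.646, a shortfall of 1.4 points.
- f = 10%: 1.0 to 1.4 points.
- f = 20%: 2.1 to 2.9 points.

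**Where the second bias reverses.** Among patients seen at exactly 3 months, dropping leaves r/(1 − S(3) + r). This equals S(24 weeks) when r = S(24 weeks)·(1 − S(3))/(1 − S(24 weeks)):
- median 9.2: 0.659 × 0.202/0.341 = 0.39;
- median 10.8: 0.701 × 0.175/0.299 = 0.41.

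Above about 39-41% response, dropping these patients pushes CBR up.

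**The case against.** A reader might infer that the SAP expressly scores ongoing stable disease as no benefit. It does not. That is the literal reading of the definition; the missing-value rules could be read to exclude these patients, and nothing says whether short follow-up counts as missing. A reader might also infer that CBR is biased down whichever way it is handled. The documents do not support that either: the drop-as-missing bias depends on the response rate and can reverse. A third option, excluding everyone with under 24 weeks of potential follow-up, removes the bias if start date is unrelated to outcome.

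The design also limits exposure. Three months is a floor. Physicians select consecutive patients from 60 days after their own first prescription, precisely to lengthen observation. With EMA approval in November 2016 and most EU collection from late 2019 or early 2020, many patients will have far more than 24 weeks. Argentina is the most exposed: fulvestrant approval in August 2016 plus 60 days allows at most about 22-26 weeks at 1 April 2017, but about 70 weeks by the end of January 2018. It supplies 162 of 2874 core records (5.6%), all partners together.

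The benchmark is approximate as well. CBR requires stable disease on therapy, so non-responders who stop early without progression would lower the true target and shrink the gap, while responders who progress early would raise it. CBR is conditional on feasibility, the analyses are descriptive, and a censored Kaplan-Meier PFS table at 3-month intervals is planned alongside.

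All of this stands and bears on size and certainty. It does not supply the missing rule. Late-adopting physicians can still contribute short follow-up, and the PFS table does not repair CBR. The separate 24-week stable-disease proportion in SAP 5.5 carries no feasibility condition.

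**Conclusion.** The mismatch is exact: 13.0 weeks of required follow-up against a 24-week criterion, for fulvestrant only, with no visible rule for patients in between. Taken literally, the definition biases the fulvestrant CBR downward and distorts the AI versus fulvestrant stratification. Dropping only ongoing stable patients replaces this with a smaller, outcome-dependent selection bias whose sign depends on the response rate.

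The figures of about 4-6 points (f = 10%) and 8-11 points (f = 20%), or about 1 and 2-3 points if dropped, rest on exponential PFS, the documents' medians and assumed f and r. They apply to the fulvestrant CBR; the effect on the overall CBR is diluted by the AI patients. The actual f is unknown and probably small in many markets. The SAP should be changed before the all-country analysis.

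**What to change.** In SAP 5.5 and 7.2.1, state that CBR and stable disease for at least 24 weeks are computed only in patients whose palbociclib combination started at least 24 weeks before the record-review date, applied by calendar date whatever the outcome. By combination partner, report:
- the number excluded by this rule;
- separately, the number within the set whose last available follow-up falls before week 24 without response, progression or death, since the date rule does not resolve them.

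Apply the same rule to the completed countries when the all-country results are produced.

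The change needs no new data and leaves eligibility alone. The cost is a somewhat smaller fulvestrant denominator and re-derivation of CBR for countries already reported, where values may differ from those delivered. The rule is unbiased only if start date is unrelated to prognosis.

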3.1. Study Objectives

Primary Objectives

1. To describe the demographic and clinical characteristics of patients who have received palbociclib combination treatments in line with locally approved indications.
2. To summarize adjuvant therapies received for the treatment of early or locally advanced breast cancer (Stages 0-IIIa).
3. To describe treatments received in the advanced/metastatic setting, before and after palbociclib combination use.
4. To describe dosing and dose changes, interruptions, delays, and discontinuations associated with palbociclib use in clinical practice.
5. To describe supportive therapies received by patients while receiving palbociclib combination treatments.
6. To determine clinical outcomes including:
 - Proportion of patients who are progression free at quarterly intervals (eg, 3, 6, 12, 18 months);
 - CCI [REDACTED]

- Objective response rate (ORR);
- Clinical benefit rate (CBR) – if feasible;
- Proportion of patients alive 1 and 2 year post palbociclib combination initiation (depending on availability of follow-up data);
- Best response (complete response, partial response, stable disease, disease progression);
- Time to death.

CCI

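### Stable disease needs no recorded assessment, so unassessed patients can count as clinical benefit, and the SAP does not say whether they should be excluded instead

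*SAP*

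**What the plan says.** SAP 7.2.1 defines CBR as the "proportion of patients achieving complete or partial response, or stable disease ≥ 24 weeks on palbociclib combination therapy", and then defines stable disease: "Stable disease will be defined as no evidence of complete or partial response, and no progression on palbociclib therapy for 24 weeks or greater". SAP 5.5 gives the same rule and lists "Proportion with stable disease ≥ 24 weeks on palbociclib" as a derived variable, not one abstracted from the record.

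Two related items do not enter the rule. Objective 6 in SAP 3.1 lists "Best response (complete response, partial response, stable disease, disease progression" as an outcome, with no 24-week condition. SAP 5.5 abstracts "Frequency with which response to palbociclib was assessed".

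On missing data, SAP 6 says: "Subjects with missing values for a particular endpoint will not contribute to the analysis of that endpoint". SAP 7.2 adds: "Percentages will be calculated excluding missing values". Neither section says whether a response that was never assessed, or is unknown, is a missing value for CBR. No CBR denominator is stated.

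Protocol 8.8 accepts an answer that the physician does not know, and plans no check against source records. The PFS definition in SAP 7.2.1 relies on "clinician-documented progression while on palbociclib". The documents set no assessment schedule.

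**The concern.** The rule infers a favourable outcome from two empty fields. A patient whose tumour was never assessed has no evidence of response and, unless progression was noted for another reason, no progression. After 24 weeks on drug she meets every word of the definition.

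A second programmer, starting from SAP 6, could treat the same patient as missing and drop her. Both would be following the SAP, and they would report different CBRs. That sits badly with the reproducibility that SAP 7.1 asks for.

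CBR falls under primary objective 6, and SAP 7.2 plans every endpoint by stratum. Protocol 8.1 presents the design as a way to compare countries directly. If countries or practice settings differ in how often they assess response, the rule could produce differences in apparent benefit that reflect assessment habits.

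**Working it through.** The documents give no CBR value and no unassessed share, so there is no planned figure to reproduce. Only the core sample size can be checked: the eCRF counts in Protocol Table 2 sum to 3131, and 3131 - 257 (German interim) = 2874, the core number in SAP 2.1.1.

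**Assumed inputs, none from the documents**
- u = share with no recorded response assessment: 5-15%.
- f = share of those on palbociclib for at least 24 weeks without recorded progression: 60-80%.
- c = CBR among assessed patients: 60-80%.

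**CBR under three treatments of the unassessed**
- Literal rule: (1 - u)c + uf
- Excluded as missing: c
- Counted as no benefit: (1 - u)c

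**Literal minus no benefit = uf**
- u = 5%: 3.0 to 4.0 points
- u = 10%: 6.0 to 8.0 points
- u = 15%: 9.0 to 12.0 points

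**Literal minus excluded = u(f - c)**
- u = 10%, c = 70%: 10% × (60% - 70%) = -1.0 to 10% × (80% - 70%) = +1.0 point
- u = 15%, extremes: 15% × (60% - 80%) = -3.0 to 15% × (80% - 60%) = +3.0 points

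With wider ranges (u 5-20%, f 50-90%), uf runs from 2.5 to 18 points. u(f - c) then runs from 20% × (50% - 80%) = -6 to 20% × (90% - 60%) = +6 points.

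**In patients.** With u = 10% and f = 70%, 2874 × 0.10 × 0.70 = about 201 core patients would enter the CBR numerator without an assessment.

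**Do ORR and CBR fit together?** Take 100 patients: 10 unassessed, 7 of whom reach 24 weeks without recorded progression; 90 assessed, with 36 responders (40%) and 27 stable for at least 24 weeks (30%), so c = 70%.

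| Treatment of the 10 unassessed | ORR | Stable ≥ 24 weeks | CBR | ORR + stable |
|---|---|---|---|---|
| Literal in both | 36/100 = 36% | 34/100 = 34% | 70/100 = 70% | 70% |
| Missing in both | 36/90 = 40% | 27/90 = 30% | 63/90 = 70% | 70% |
| Missing for ORR, literal for CBR | 36/90 = 40% | 34/100 = 34% | 70/100 = 70% | 74% |
| No benefit in both | 36/100 = 36% | 27/100 = 27% | 63/100 = 63% | 63% |

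Only the mixed reading fails to add up. In this example f = c, so the literal rule and exclusion give the same CBR.

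**A separate effect in the other direction.** The SAP requires only three months of follow-up with fulvestrant. At 30.4 days per month that is 3 × 30.4 / 7 = 13.0 weeks. A non-responder followed for 13 to under 24 weeks cannot yet qualify as stable and lowers CBR if she stays in the denominator. If 5-20% of patients are in that position and stable disease supplies 30 points of CBR (both assumed), the effect is -1.5 to -6.0 points.

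**The case against.** The strongest reply is that SAP 6 already covers this. If an unassessed response is a missing value, the patient leaves both ORR and CBR, the two rates share a denominator, and no one is misclassified. That reading is available. It is not secure, because stable disease is derived: an empty response field satisfies the no-evidence condition, so the derivation returns stable rather than missing. The SAP has to say which applies.

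A reader might infer that CBR is inflated by 3-12 points. The documents do not support that. The figure rests on assumed shares and on counting unassessed patients as no benefit, which SAP 6 does not do. Against exclusion the sign is open, and short fulvestrant follow-up can pull CBR down. A reader might also infer that the plan makes the same patient a CBR success while leaving her out of ORR. That is only one of the possible readings.

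Three further points stand in part. SAP 7.2 will show missing and unknown categories, so some of the problem will be visible to readers. Making no benefit the main rule would conflict with the SAP 6 policy against imputation, so that count belongs in a sensitivity analysis. The recorded stable-disease category appears in SAP 3.1 as an objective, while the abstracted items in SAP 5.5 name initial, complete and partial response. The eCRF is not among the documents, so its response categories need confirming.

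**Conclusion.** The point holds as a defect in a stated rule. The definition lets a patient with no recorded assessment be classed as stable disease and clinical benefit, and the missing-data sections do not clearly prevent it. CBR can therefore be misstated, and ORR and CBR can end up on different denominators.

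The size is conditional. It is 3-12 points above a no-benefit count if u is 5-15% and f is 60-80%. Against exclusion it is between -3 and +3 points on the same ranges with c at 60-80%, and -6 to +6 on the wider ones. The direction of any error against exclusion cannot be settled from the documents.

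The change is worth making but does not threaten the study: CBR is descriptive and SAP 3.1 makes it conditional on feasibility.

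**What to change.** In SAP 5.5 and 7.2.1:

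1. Define stable disease of at least 24 weeks as at least one recorded response assessment showing stable disease (no complete response, partial response or progression) **and** at least 24 weeks on palbociclib without progression.
2. Report patients with no recorded assessment as a separate not-assessed category, never in the CBR numerator.
3. Use one denominator for ORR and CBR. Main analysis: assessed patients, consistent with SAP 6. Sensitivity analysis: all patients, with the unassessed counted as not shown to benefit.
4. State how non-responders with under 24 weeks of follow-up enter the CBR denominator, and whether a documented progression alone counts as an assessment. If it does not, such patients would leave the main denominator.

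Before finalising, confirm that the eCRF records stable disease as a response category, including in the countries where collection is complete.

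The cost is SAP wording and a few more lines of code, a smaller denominator for the main CBR, and a less favourable CBR in the all-patient sensitivity analysis. If the response category is confirmed, no new data are needed.

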5.3. Clinical Characteristics

To be abstracted directly from the medical records:

- Date of initial breast cancer diagnosis;
- Stage at initial breast cancer diagnosis;

-
- Date of ABC/mBC diagnosis;
 - Stage of ABC/mBC diagnosis (eg, locoregionally advanced or metastatic);
 - Site of metastases at metastatic diagnosis;
 - Degree of involvement of metastases (eg, single vs. multiple lesions);
 - Patient's performance status at initiation of palbociclib, as scored using the Eastern Cooperative Oncology Group scale or Karnofsky scale;
 - Patient's current performance status, if applicable;
 - Family history of breast cancer;
 - Biomarker status (BRCA, Androgen receptor, ESR1 mutation);
 - Comorbidities diagnosed in the 12 months prior to palbociclib initiation.

To be Derived:

- Time from initial breast cancer diagnosis to ABC/mBC diagnosis.

5.4. Prior Treatment for Early Breast Cancer**To be abstracted directly from the medical records:**

- Category of treatment received (eg, surgery, radiotherapy, neoadjuvant treatment, adjuvant chemotherapy, adjuvant endocrine therapy);
- Adjuvant endocrine therapy start and end dates;
- Reason for stopping adjuvant endocrine therapy (eg, regimen complete, disease recurrence, patient preference, side effects/toxicity, other).

To be Derived:

- Duration of adjuvant endocrine therapy;
- Disease Free Interval, defined as time from regimen completion of adjuvant therapy to diagnosis of ABC/mBC.

5.5. Treatment Patterns for Advanced or Metastatic Breast Cancer**To be abstracted directly from the medical records:**

- Number of lines of therapy received for ABC/mBC at the time of medical record abstraction;

-
- Treatment(s) received in each line of therapy;
 - Start and stop dates of each treatment within each line of therapy;
 - Receipt of palbociclib therapies, by combination partner;
 - Reason for regimen end (eg, disease progression, disease progression following initial control/response, Disease progression without initial control/response, Treatment cost, pill burden/compliance, side effects/toxicity, patient request, other);
 - Date of disease progression for each regimen (if applicable).

To be derived:

- Time from initial breast cancer diagnosis to palbociclib initiation;
- Time from advanced/metastatic diagnosis to palbociclib initiation;
- Duration of each line of therapy;
- Duration of ongoing and discontinued palbociclib treatment;
- Distribution of therapies received post palbociclib discontinuation;

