Number of interruptions	Primary objective 4	CRF H3b	Including zeros, ie, no interruptions
Duration of interruptions	Primary objective 4	CRF H3a	
Any cycle delays?	Primary objective 4	CRF H3b	
Duration of cycle delays	Primary objective 4	CRF H3a	
Reasons for dose change	Primary objective 4	CRF H3c	Multiple responses allowed. Reduce to patient level, ie, if “lack of response” is ticked for any dose changes then “lack of response” is considered ticked
Status of combination partner therapy when dose is changed	Primary objective 4	CRF H3d	
Time from palbociclib initiation to first dose change	Primary objective 4	CRF H3a	

Table 5. Supportive Therapies Whilst Receiving Palbociclib

Variable	Role	Data source(s)	Operational definition
All supportive therapies received whilst receiving palbociclib	Primary objective 5	CRF H4	Multiple responses allowed

Table 6. Clinical Outcomes

Variable	Role	Data source(s)	Operational definition
CCI			
Progression free survival	Exploratory objective	CRF G2e	Defined as the time from the start of palbociclib to the first subsequent progression or death. The treatment grid in section G will be used to determine in which treatment line that this occurs.
Progression free at 6, 12, 18, 24 months of treatment	Primary objective 6	CRF G2e	Proportion of patients who have not displayed progression at defined time points.
Did the patient achieve complete response whilst receiving palbociclib?	Primary objective 6	TBC	
Time to complete response	Primary objective 6	TBC	
Did the patient achieve partial response whilst receiving palbociclib?	Primary objective 6	TBC	
Time to partial response	Primary objective 6	TBC	
Objective Response Rate	Primary objective 6	CRF I1d/I1e	Proportion of patients who achieve CR/PR at CRF I1d/I1e.

Variable	Role	Data source(s)	Operational definition
Time to Death	Primary objective 6	CRF B7	This will be the time from the start of palbociclib to death. This will only include patients for whom death has been recorded.
CCI			
Survival at 12, 18, 24 months	Primary objective 6	AQ2, BQ7	Proportion of patients who have not died at defined time points.

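### SAP 7.2.1 counts progression only on palbociclib yet keeps patients at risk afterwards; SAP 5.5 and Appendix 1 Table 6 set no such limit, so PFS has two definitions and 7.2.1 overstates it

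*SAP*

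**What the plan says.** Three current SAP texts define PFS.

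- **SAP 7.2.1** takes the first of these as the event: "1) clinician-documented progression while on palbociclib (2) death, (3) start of a new therapy line after final palbociclib dose if the reason for discontinuation". Item (3) applies only where the drug was stopped because of progression. On censoring it says: "Patients who did not experience a progression event (items 1, 2 and 3) will be censored at date of last available follow-up". Nothing ends the time at risk when palbociclib stops.
- **SAP 5.5 (Clinical Outcomes, derived variables)** has PFS "defined as the time from the start of palbociclib to the first subsequent progression or death". It sets no on-drug limit.
- **SAP Appendix 1, Table 6** repeats the 5.5 definition, gives CRF G2e (progression date per regimen) as the source, and adds: "The treatment grid in section G will be used to determine in which treatment line that this occurs".

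The progression-free proportions are also worded in two ways. Table 6 titles them "Progression free at 6, 12, 18, 24 months of treatment", whereas SAP 5.5 has them "defined as the proportion of patients who have no documented progression at defined time points". SAP 7.2 says that time-dependent event rates "will also be reported based on lifetables derived from the Kaplan-Meier analyses".

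SAP 5.5 expects palbociclib to stop for reasons other than progression: "Treatment cost, pill burden/compliance, side effects/toxicity, patient request, other".

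**The concern.** Section 7.2.1 limits one half of the estimator and not the other: progression counts only on drug, but time at risk runs on after the drug stops. A patient who stops for toxicity, cost, compliance or by request and then progresses on her next line meets none of items (1) to (3) at that progression. She stays in the risk set as progression-free, and only death can then count as her event. This lifts the curve, the median and the 3-monthly rates above true PFS.

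Section 5.5 and Table 6 would count the same progression, so two programmers following one SAP could report different medians.

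Neither text is complete. Item (3), the fallback for patients who stopped for progression, exists only in 7.2.1. The Table 6 source column names G2e alone and not the stop reason (G2d) that item (3) needs.

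**Working it through.** **Reading the rules side by side**

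| Patient | SAP 7.2.1 | SAP 5.5 / Table 6 |
|---|---|---|
| Stops for toxicity at month 4, progresses on next line at month 9, alive at month 20 | Censored at 20 months | Event at 9 months |
| Progresses on palbociclib, no date recorded, starts a new line | Event at start of new line (item 3) | No date to use: dropped under SAP 6, or moved to the next recorded progression or death |

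The first row is the upward bias. The second shows that 5.5, programmed from G2e alone, has a gap of its own.

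**Size of the bias against true PFS**

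The documents state no PFS result to reproduce. I take two cited trial medians from Protocol section 6 as illustrative true values: 10.8 months (fulvestrant partner) and 24.8 months (letrozole partner).

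Assumptions not in the documents:
- exponential times;
- a share p of palbociclib stops (5, 10, 20 or 30%) is for non-progression reasons, unrelated to prognosis;
- the same progression hazard on and off drug;
- median survival after progression of 18 months;
- no deaths before progression.

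Hazards per month: λ = ln2/median, σ = λp/(1−p) for non-progression stops, μ = ln2/18 = 0.0385.

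The curve under 7.2.1 is the true curve plus the patients who have progressed off drug and are still alive:

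S₇₂₁(t) = e^(−λt) + C(t), where

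C(t) = λ·[ (e^(−μt) − e^(−λt))/(λ−μ) − (e^(−μt) − e^(−(λ+σ)t))/(λ+σ−μ) ].

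C(t) is never negative, and it is zero when p = 0.

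Worked value, median 10.8, p = 20%, t = 18: λ = 0.06418, σ = 0.01605. C(18) = 0.06418 × [(0.5000 − 0.3150)/0.02567 − (0.5000 − 0.2360)/0.04172] = 0.06418 × (7.207 − 6.328) ≈ 0.056. So 18-month PFS reads 31.5% + 5.6% = 37.1%.

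| Quantity under 7.2.1 | True | p = 5% | 10% | 20% | 30% |
|---|---|---|---|---|---|
| Median, months | 10.8 | 11.0 | 11.3 | 12.0 | 13.0 |
| 18-month PFS, % | 31.5 | 32.8 | 34.1 | 37.1 | 40.6 |
| Median, months | 24.8 | 25.2 | 25.7 | 26.9 | 28.5 |
| 18-month PFS, % | 60.5 | 60.8 | 61.2 | 62.2 | 63.3 |

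If half of the off-drug progressions are entered under the palbociclib regimen, and so caught by item (1), C(t) halves. The medians become 10.9 / 11.0 / 11.3 / 11.7 and 25.0 / 25.2 / 25.8 / 26.5.

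**Cross-check.** A separate simulation (400,000 patients per scenario) used annual stop rates, 5% or 10% of first events as deaths, and 24-month median survival after progression. At 5, 10 and 20% of patients stopping per year, the 24.8-month median becomes about 26, 27.3–27.6 and 30.7–31.5. The 10.8-month median becomes 11.0–11.1, 11.4 and 12.0–12.2. With no such stops the two definitions agree exactly.

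**7.2.1 against 5.5 when some on-drug progressions are undated.** This was simulated with follow-up uniform over 3–36 months, 10% of on-drug progressions undated, a new line 1 month after progression, and undated patients dropped under 5.5. Error is about 0.2 months in the 24.8-month case.

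| Rule | True 10.8: p = 5 / 10 / 20 / 30% | True 24.8: p = 5 / 10 / 20 / 30% |
|---|---|---|
| 7.2.1 | 11.1 / 11.4 / 12.1 / 13.1 | 25.2 / 25.8 / 27.1 / 28.7 |
| 5.5 from G2e only | 11.3–11.4 throughout | 26.6–26.8 throughout |
| Any line, item (3) mandatory | 10.9 | 24.8–25.0 |

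So 5.5 gives the higher median at 5% stops, the order is mixed at 10%, and 7.2.1 is higher at 20–30%. The any-line rule with the fallback stays close to the truth throughout.

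**The case against.** - **An on-treatment measure may be intended.** The on-drug wording in 7.2.1, the similar wording of clinical benefit rate, and the Table 6 title for the progression-free proportions all fit that reading. It would be legitimate, but it needs censoring at the end of palbociclib, which 7.2.1 does not do.
- **Last available follow-up is undefined.** If it meant follow-up on palbociclib, the at-risk problem would shrink. The text does not say so, and the conflict with 5.5 and Table 6 would remain.
- **Table 6 points to the whole section G grid, which holds stop reasons and line dates.** True, but that sentence only locates the line in which progression occurs. It supplies no fallback rule.
- **Undated progressions may be rare.** Protocol 8.8 makes every eCRF question mandatory and expects no missing data. It also accepts unknown as an answer, so the case can arise. The 10% rate is an assumption.
- **The effect is small at low stop rates.** At 5–10% the median moves by 0.2–0.5 months (10.8) or 0.4–0.9 months (24.8). The sampling range of a median from 250 patients, with the same 3–36 month follow-up, is roughly 9 to 13 months and 20 to 30 months or more. This stands as a limit on importance. A bias does not average out, however, and it carries into the pooled estimate, where sampling error is smaller.
- **PFS is labelled exploratory and the study is descriptive.** Also true. The primary progression-free proportions are affected only if they are read from the same lifetable.

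**Conclusion.** The concern holds. The conflict between 7.2.1 and 5.5 / Table 6 is in the text and depends on no assumption. Against true PFS, 7.2.1 can only err upward: some patients who have already progressed stay at risk, and none is counted early. The bias is zero without non-progression stops and grows with their share.

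Its size cannot be fixed from the documents, which give no share of such stops, no share of undated progressions and no survival after progression. For shares of 5–30%, the illustrative excess in the median is 0.2–2.2 months on 10.8 and 0.4–3.7 months on 24.8, and about half that if half of off-drug progressions are still caught. The claim is about true PFS. Against 5.5 programmed from G2e alone, the gap can be smaller or reversed. This should be fixed before the all-country analysis.

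**What to change.** Write one definition into SAP 5.5, SAP 7.2.1 and Appendix 1 Table 6:

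1. Event = earliest documented progression in any line (CRF G2e) or death. Remove the on-drug restriction from item (1) of 7.2.1.
2. Keep item (3) as a mandatory fallback in all three places. If palbociclib was stopped for progression and no date is recorded, the event date is the start of the next line, and a later-line progression date must not replace it.
3. Add to the Table 6 PFS row the sources this needs: G2d (stop reason), G2b/c (line dates) and B7 (death).
4. State that the progression-free proportions at 3 to 24 months use the same rule, and define last available follow-up.
5. Report how many events come from G2e, from the fallback and from death, and how many stops for progression have neither a date nor a new line.

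If an on-treatment measure is wanted instead, name it as such, censor at the end of palbociclib, state the non-informative-stopping assumption, and report the any-line version beside it. In the simulations this gave 10.9–11.0 and 24.8–25.1 months when stopping was unrelated to prognosis.

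The cost is SAP wording in three places and a small programming change. Progression dates, line dates, stop reasons and deaths are already collected. Relative to 7.2.1 as written, reported PFS would become slightly less favourable.
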